11.3 Expedited Expected Adverse Event Reporting Exclusions

For this protocol, the following adverse events are specifically excluded from expedited AE reporting: **None**

Note: All deaths on study will be reported using expedited reporting regardless of causality. Attribution to treatment or other cause will be provided.

Fatal and life-threatening events will be reported to the IRB within 24 hours of notification of the event, indicating that a full report will follow. Any unexpected fatal or life threatening adverse experience associated with the use of [¹⁸F]Flutemetamol will be reported to the FDA by telephone or fax no later than 7 calendar days after initial receipt of the information. All reportable adverse

events will be submitted to the FDA & IRB within the required timeframe by as mandated by the FDA and IRB.

11.4 Data Reporting

A Data and Safety Monitoring (DSMC) is established at Huntsman Cancer Institute (HCI) and approved by the NCI to assure the wellbeing of patients enrolled on Investigator Initiated Trials that do not have an outside monitoring review. Roles and responsibilities of the DSMC are set forth in the NCI approved plan. The activities of this committee include a quarterly review of adverse events including SAEs, important medical events, significant revisions or amendments to the protocol, and approval of cohort/dose escalations. If the DSMC and/or the PI have concerns about unexpected safety issues, the study will be stopped and will not be resumed until the issues are resolved. The DSMC also reviews and approves audit reports generated by the Research Compliance Office.

This study is considered a low risk trial per the DSMC plan. All low risk studies are audited no less than annually by the Research Compliance Office and audit reports will be reviewed and approved by the full DSMC. The DSMC will also review all Serious Adverse Events for patients on this study.

11.5 Reporting Protocol Violations/Deviations

A protocol deviation (or violation) is any departure from the defined procedures and treatment plans as outlined in the protocol version submitted and previously approved by the IRB. Protocol deviations have the potential to place participants at risk and can also undermine the scientific integrity of the study thus jeopardizing the justification for the research. Protocol deviations are unplanned and unintentional events.

Because some protocol deviations pose no conceivable threat to participant safety or scientific integrity, reporting is left to the discretion of the PI within the context of the guidelines below.

The IRB requires the prompt reporting of the following protocol deviations:

- Exceptions to eligibility criteria
- Intended to eliminate apparent immediate hazard to a research participant or
- Harmful (caused harm to participants or others, or place them at increased risk of harm - including physical, psychological, economic, or social harm) or
- Possible serious or continued noncompliance

Annual progress reports will be submitted to the FDA within 60 days of the date that the IND was effective/or approved.

12. ETHICAL AND REGULATORY REQUIREMENTS

12.1 Informed consent

Informed consent will be obtained from all research participants prior to performing any study procedures using the most recent IRB approved version.

12.2 Institutional Review

This study will be reviewed and approved by the Institutional Review Board of University of Utah prior to any participants being enrolled on the study.

12.3 Reported Adverse Events and Potential Risks

Blood sampling entails the risks of minor discomfort, infection, bruising and bleeding. Radiation risk accompanies the use of radioisotopes in PET imaging. FDG-PET imaging is considered to be generally safe and effective. It has been approved by the Centers for Medicare and Medicaid for several clinical indications, using procedures identical to those used in this study. FDG is administered in trace doses and adverse effects have not been reported during its more than 20 years of use. Nevertheless the possibility exists for a rare allergic reaction.

The current use of [¹⁸F]Flutemetamol is investigational although it did receive FDA approval in October 2013. To date, it has been given to numerous individuals world-wide at the doses proposed here without significant adverse effect.¹²² Subjects scanned with PET are exposed to radiation. The amount of radiation exposure will be well within limits permitted to radiation workers by federal regulations. There is no known minimum level of radiation exposure that is recognized as being totally free of the risk of causing genetic defects (cellular abnormalities) or cancer. However the risk associated with the amount of radiation exposure that the subject will receive from this study is considered to be low.

Radioisotope injection requires the use of an intravenous catheter. There is a minimal risk of infection and bruising associated with the venipuncture required for the indwelling catheter. There can be discomfort from the requirement from lying quietly during imaging. Research data includes personal health information that can be inadvertently revealed to others. All of these risks are similar to those encountered during usual clinical care.

For the MRI, the risks are expected to be minimal. There is a protocol to follow prior to imaging, which includes a rigorous screening by specially trained MR personnel to avoid the risks listed below. All MR imaging will occur in the Imaging and Neurosciences Center at the University of Utah under the supervision of a Neuroradiologist. If individuals have any MRI incompatible metal pieces in their body, these metal pieces could potentially move during the scan and damage nearby tissues or organs. Transdermal patches also may contain metal and may cause burns if they are not removed from the skin before the scan. There can be a feeling of claustrophobia associated with the procedure; if participants experience anxiety from a feeling of claustrophobia, they can tell the researcher. Individuals can be removed from the scanner and given the option to terminate the study, if they become uncomfortable for any reason.

We will strive to maintain confidentiality of all participants enrolled in the study. All paper research data will be stored in a locked file cabinet. All electronic data will be stored on password-protected computers. All research data will be de-identified. Finally, all participants will be assigned a unique identification number to use in place of their name on all study data.

12.4 Agent Accountability

Each radiosynthesis is done by University of Utah cyclotron and radiochemistry staff and the product [¹⁸F]Flutemetamol in a dose calibrated syringe will be released after passing all required quality control assays to the physician who will be responsible for administering the appropriate amount ([name] or his designee). The quality control tests that must be passed prior to release of the product [¹⁸F]Flutemetamol for injection include the radioactive purity, the radiochemical purity, sterilizing filter integrity, pyrogens, and particulates. The [¹⁸F]Flutemetamol dose is drawn up into a syringe, assayed for mCi at the time of injection, and administered to the research subject. Any remaining compound from the synthesis will be allowed to decay and destroyed per our facilities standard operating procedures.

12.4.1 [¹⁸F]Flutemetamol

Flutemetamol is a radiopharmaceutical that is produced in the cyclotron facility at the Huntsman Cancer Institute. The agent is investigational and approved by the FDA under IND #109,760.

12.4.2 [¹⁸F]FDG

FDG is a radiopharmaceutical that is produced in the cyclotron facility at the Huntsman Cancer Institute. The agent is investigational and approved by the FDA under IND # 113,858.

14. APPENDICES

APPENDIX A

Eligibility Check List and Current Drug Use and Potential Toxicities

APPENDIX B

Current Drug Use and Potential Toxicities

APPENDIX C

MRI Patient History and Safety Screening

APPENDIX D

Schedule of Events

APPENDIX E

[¹⁸F] Flutemetamol Patient Adverse Event Questionnaire

GE Healthcare Pregnancy Reporting Form

APPENDIX F

NCI Common Toxicity Criteria

APPENDIX G

GE Healthcare Pregnancy Reporting Form

APPENDIX H

GE Healthcare SAE Reporting Form

APPENDIX I

GE Healthcare Supplemental Safety Reporting Form

APPENDIX A: Eligibility Check List and Current Drug Use and Potential Toxicities

Patient Name: _____ Date: _____

MRN: _____ Person Confirming Eligibility _____

 (Yes/No) Patient is female. (Yes/No) Patient is \geq 18 years old. (Yes/No) Patient is \leq 70 years old. (Yes/No) Patient has a histologically proven diagnosis of Stage I through III C breast cancer (Yes/No) Patient has been previously treated with chemotherapy at least 6 months prior, but no more than 36 months prior to initial study scan.

Dates: _____

Type of Chemotherapy: _____

 (Yes/No) Patient must be postmenopausal for a minimum of one year, surgically sterile, or has been confirmed not to be pregnant by serum pregnancy test performed within 48 hours prior to research PET imaging.

If patient is postmenopausal, how far out are they from menopause: _____

If patient is of childbearing potential, date of negative pregnancy test: _____

 (Yes/No) Patient is not lactating. (Yes/No) Patient has no history of previous stroke, seizures, or other neurological disorders. (Yes/No) Patient agrees to have clinical and radiographic endpoints and results of histopathologic tissue analysis and other laboratory information entered into a research database, as evidenced by signing the informed consent form. (Yes/No) Patient does not have allergic or hypersensitivity reactions to previously administered radiopharmaceuticals. (Yes/No) Patient does not require monitored anesthesia for PET scanning or MRI imaging.

(Yes/No) Patient is not too claustrophobic to undergo MRI or PET imaging.

(Yes/No) Patients is able to lie still for 60 minutes.

(Yes/No) Patient does not have any MRI incompatible metal implants or clips.

(Yes/No) Patient has not been diagnosed with dementia or any other cognitive deteriorating conditions.

(Yes/No) Does patient have a family history of dementia? (Does not preclude participation in study)

(Yes/No) Is the patient right handed? (Informational for set up of fMRI study)

(Yes/No) Patient is not moderately or severely depressed as measured on the Beck Depression Inventory (BDI) –Short Form.

(Yes/No) Patient must report persistent cognitive problems following the initiation of chemotherapy, defined as being one or more standard deviations above normative data on our two scales of subjective cognitive dysfunction

- Cognitive Failure Questionnaire Score: _____ (Total score 45 or higher) _____
- Frontal System Behavioral Scale Score: _____ (T-score of 60 or higher) _____

(Yes/No) Patient is not currently using gabapentin or venlafaxine for hot flashes.

(Yes/No) Patient is not currently using cholinesterase inhibitors, other cognitive enhancers, antipsychotics, antidepressants or anticonvulsant medications.

(Yes/No) Patient is not color blind.

(Yes/No) Patient has no history of radiation therapy to the brain, any current or past major psychiatric illness, or a history of alcoholism or other substance abuse.

(Yes/No) Patient does not have a current or past major psychiatric illness such as schizophrenia or bipolar affective disorder.

PI: [name]

Page 59 of 73

Title: Amyloid Plaque Deposition in Chemotherapy-Induced Cognitive Impairment

IND Number: [¹⁸F]Flutemetamol – IND # 109,760, FDG – IND # 113,858

Previous Version Date: 01/11/2021

Version Date: 03/21/2024

Comments:

I certify that this patient meets all inclusion and exclusion criteria for enrollment onto this study.

Investigator Signature

Date

Time

Appendix B: Current Drug Use and Potential Toxicities**Current Drug Use and Potential Toxicities**

Drug	Neuropathy	Hematologic	Hepatic	Other prominent toxicity (note it)

Completed by _____ Date: _____

APPENDIX C: MRI Patient History and Safety Screening

MRI PATIENT HISTORY & SAFETY SCREENING

Please print

Date _____

Patient MRN _____

Name _____

Patient Height _____ Weight _____

Date of Birth _____ Age _____ ReferringPhysician _____

DO YOU HAVE AN APPOINTMENT WITH YOUR DOCTOR TODAY? _____ If yes, at what time? _____

IMPORTANT INSTRUCTIONS: You may be asked to change into hospital clothing for purposes of MRI safety. A locker will be provided. Please remove ALL metallic objects such as hearing aids, dentures, partial plates, keys, cell phone, eyeglasses, hair pins/clips, jewelry, body piercing jewelry, watch, safety pins, magnetic strip cards and clothing with metallic fasteners, threads or fibers including some sportswear tech fabrics. If you have any questions, please ask a technologist BEFORE entering the MRI scan room.

 Yes	 No	Cardiac Pacemaker (If yes, Stop and inquire with MRI personnel)
 Yes	 No	Implanted Cardiac Defibrillator (ICD) (If yes, Stop and inquire with MRI personnel)
 Yes	 No	Breast Tissue Expanders (If yes, Stop and inquire with MRI personnel)
 Yes	 No	Spinal cord stimulator (If yes, Stop and inquire with MRI personnel)
 Yes	 No	Swan-Ganz Thermo Dilution catheter (If yes, Stop and inquire with MRI personnel)
 Yes	 No	Acticoat Silver Wound Dressing (If yes, Stop and inquire with MRI personnel)
 Yes	 No	Cochlear Inner Ear Implant (If yes, Stop and inquire with MRI personnel)
 Yes	 No	Stapes Inner Ear Implant
 Yes	 No	Brain Aneurysm Stents, Clips or Coils Type _____
 Yes	 No	Electronic or Magnetic Implant, Neurostimulator (tens unit, bone growth, etc.)
 Yes	 No	Internal electrodes or wires
 Yes	 No	Aortic or Carotid Artery Clips
 Yes	 No	Hearing Aid (Remove before entering MRI scan room)
 Yes	 No	Insulin pump or Implanted Infusion device Type _____
 Yes	 No	Heart Valve or Cardiac Stent
 Yes	 No	Shunt, intraventricular or spinal
 Yes	 No	Vascular Coil, Umbrella Filter, or other Stent
 Yes	 No	Vascular Access Port or I.V. Catheter
 Yes	 No	Prosthetic device (Limb, Joint, Eye, etc.) Type _____
 Yes	 No	Joint replacements (Hip, Knee, etc.) Location _____
 Yes	 No	Metal (circle) Rods, Plates, Screws, Nails, Pins, Clips, Other Location _____
 Yes	 No	Shrapnel (Metal Fragments) or Gunshot Injury Location _____
 Yes	 No	Metal Fragments in eye past or present (History as Grinder, Welder, Machinist, etc.)
 Yes	 No	IUD, Diaphragm, Penile Implant
 Yes	 No	Eyelid Spring, Wire, Gold Weight
 Yes	 No	Medication Patch (Remove before entering MRI scan room)
 Yes	 No	Wire Mesh Implant
 Yes	 No	Removable Denture or Retainer
 Yes	 No	Tattoos (Cosmetic, Body)
 Yes	 No	Body Piercings Location _____

Yes No Biopsy Markers or Breast Implants: Type _____

Yes No Hair Pins or Hair Piece / Wig (*Will need to be removed before entering MRI scan room*)

Yes No Bronzing / Tanning Lotions

Yes No Other Implants (Pill Camera, Tooth, etc.) Type _____

I attest that the above information is correct to the best of my knowledge. I read and understand the contents of this form and had the opportunity to ask questions regarding the information on this form and regarding the MR procedure that I am about to undergo.

Signature of Person Completing Form: _____

Print Name: _____

Date: ____ / ____ / ____

Form Completed By: Patient Guardian Relative Nurse/Physician

APPENDIX D: Schedule of Events

Test / Procedure	Screen	Research MRI study and Neuro-psychological Testing	PET Imaging Visit 1 First PET Exam Will depend on whether [¹⁸ F]-Flutemetamol or FDG study is performed	PET Imaging Visit 2 Second PET Exam Will depend on whether [¹⁸ F]-Flutemetamol or FDG study is performed
Inclusion / Exclusion Criteria	X			
Informed Consent	X			
Research MRI study		X		
Infusion of [¹⁸ F]Flutemetamol			X	X
[¹⁸ F]Flutemetamol PET Imaging			X	X
Adverse Event Questionnaire After [¹⁸ F]Flutemetamol study			X (3)*	X (3)*
¹⁸ F-FDG PET Imaging			X	X
Neuropsychological Testing		X		
Pregnancy Test (1)			X (2)	X (2)

* Performed immediately after [¹⁸F]Flutemetamol study

1 Patient must be postmenopausal for a minimum of one year, surgically sterile, or has been confirmed not to be pregnant by serum pregnancy test performed within 48 hours prior to research PET imaging.

2 GE requires all pregnancies that occur within 30 days of exposure to the investigational product be submitted to their institution. Patients will be contacted approximately 30 days post [¹⁸F]Flutemetamol scanning to collect information from the patient regarding pregnancy status.

3 A follow-up telephone call will be made to each participant within 1 day following their imaging scan with [¹⁸F]Flutemetamol. If the participant cannot be contacted at 1 day post-scanning, then we will continue trying to contact them for up to 7 days post-scanning.

4 The research MRI study and neuropsychological testing can be completed depending on staff availability and can be done before, after, or in between PET/CT imaging sessions.

Research MRI study

The research MRI study will include the following imaging sequences/studies. This is our current clinical brain tumor imaging protocol.

Scout

T1-weighted SE (pre injection)

T2

FLAIR;

Dynamic contrast enhanced images with associated T1 mapping

Diffusion- weighted imaging

Post T1-weighted SE

PET Imaging Visits 1 & 2:

Imaging of the PET tracers will be performed on two separate days with FDG imaging occurring on one day and [¹⁸F]Flutemetamol occurring on another day. The imaging will be performed on separate days depending on scheduling with the cyclotron. The days of imaging will be scheduled according to scanner and cyclotron availability, and all days of imaging will be obtained within six weeks of each other.

APPENDIX E: [¹⁸F]Flutemetamol Patient Adverse Event QuestionnaireCompleted at conclusion of [¹⁸F]Flutemetamol infusion.

Subject Name and MRN: _____ Subject Study ID (if enrolled) _____

Projected Study Start Date _____ Referring MD _____

Possible Adverse Event	Y = Yes	Comment on possible AE
N = No		
Body as a Whole:		
Pain (Abdominal)		
Pain (Chest/Breast)		
Pain (Other site)		
Fever		
Injection site reaction		
Cardiovascular System:		
Vasodilation (flushing)		
Digestive System:		
Nausea		
Diarrhea		
Vomiting		
Respiratory System:		
Dyspnea (Shortness of breath)		
Skin and Appendages:		
Rash		
Pruritus (Itching)		
Urticaria (Hives)		
Sweating		
Cyanosis (discoloration of fingers/toes)		
Central Nervous System		
Visual disturbances		
Numbness of feet		
Numbness of fingers/hands		
Weakness of feet		
Weakness of fingers		
Burning sensation in feet		
Burning sensation of fingers		

Performed by _____ Date _____ Time _____

PI Oversight _____ Date _____ Time _____

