Of the 23 subjects who received [¹¹C]Flutemetamol or [¹¹C]Flutemetamol and [¹⁸F]AH110691, 2 subjects (9%) experienced AEs within the MedDRA body system of 'nervous system disorders'. No other body system was evidenced in more than 1 subject. The most frequent AE was 'headache' (2 subjects). The remaining 2 AEs, which occurred in 1 subject each, were 'injection site extravasation' and 'vomiting'. The 'injection site extravasation' AE was actually a procedural complication with the arterial line used to take arterial blood samples and is not related to the drug product.

Two AEs required action to be taken. One subject had the arterial line removed due to injection site extravasation' and 1 subject was given medication for a headache. Examination of the occurrence of AEs, their intensities, and relationship to [¹¹C-] Flutemetamol and/or [¹⁸F]AH110691 across the subject groups revealed no safety signal.

Based on the number and nature of the AEs and the fact that no SAEs occurred, the results of The ALZ101 study indicate [¹¹C]Flutemetamol to be safe and well tolerated. There was no specific profile for occurring AEs. The few AEs reported were primarily mild in intensity, resolved during the study, were deemed to be unrelated to [¹¹C]Flutemetamol and did not result in withdrawals. Assessment of laboratory parameters for hematology, serum biochemistry and urinalyses, as well as vital signs and ECGs revealed no trends or other signals that were indicative of a safety concern.

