8.3 Inclusion Criteria

- Female patients must be 18 years or older for inclusion in this research study. There is inadequate experience with the safety of [¹⁸F]Flutemetamol in children and therefore this radiopharmaceutical should not be used in patients under the age of 18. Individuals over 70 years age will be excluded as the incidence of amyloid positivity increases significantly even with no cognitive problems and will not allow for testing of our primary hypothesis.
- The patient must have a histologically proven diagnosis of Stage I through IIIC Breast Cancer.
- The patient must have completed adjuvant chemotherapy more than 6 months ago, but no more than 36 months prior to initial study scan.
- The patient must report persistent cognitive problems following the initiation of chemotherapy, defined as being one or more standard deviations above normative data on our two scales of subjective cognitive dysfunction. This is defined as a total score of 45 or higher on the Cognitive Failure Questionnaire, and a T-score of 60 or higher on the Frontal System Behavioral Scale Questionnaire.
- Patients must agree to have clinical and radiographic endpoints and the results of histopathologic tissue analysis and other laboratory information entered into a research database, as evidenced by signing the informed consent form.
- All patients, or their legal guardians, must sign a written informed consent and HIPAA authorization in accordance with institutional guidelines.

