11. REGULATORY AND REPORTING REQUIREMENTS

This study involves exposure to radiation and is appropriate for Human Use Subcommittee Review. FDG-PET is a clinically approved procedure for patients with cancer. However, for this research study, FDG is being performed under IND# 113,858 and [¹⁸F]Flutemetamol is being performed under IND#109,760 ([name] is IND holder for both INDs), as such the following FDA reporting of unexpected fatal or life threatening events, serious adverse events, and serious and unexpected adverse events will occur: (1) reporting any unexpected fatal or life threatening adverse experience associated with the use of [¹⁸F]Flutemetamol by telephone or fax no later than 7 calendar days after initial receipt of the information. (2) Reporting any adverse experience associated with the use of [¹⁸F]Flutemetamol, that is both serious (SAE) and unexpected in writing

no later than 15 calendar days after initial receipt of the information. (3) Submitting annual reports. The reportable events will also be submitted to the IRB using the University of Utah ERICA online system:

<https://erica.research.utah.edu/erica/Rooms/DisplayPages/LayoutInitial?Container=com.webridge.entity.Entity%5B0ID%5B5FD2DA60262617429607E459C0E09D92%5D%5D>

The descriptions and grading scales found in the revised NCI Common Terminology Criteria for Adverse Events (CTCAE) version 4.03 will be utilized for adverse event reporting (<http://ctep.cancer.gov/reporting/index.html>).

All appropriate research areas will have access to a copy of the CTCAE version 4.03 with modifications. A list of adverse events that have occurred or might occur (Reported Adverse Events and Potential Risks) can be found in Section 6 (Imaging Studies Information).

The reportable events will also be submitted to the IRB using the University of Utah ERICA online system:

<https://erica.research.utah.edu/erica/Rooms/DisplayPages/LayoutInitial?Container=com.webridge.entity.Entity%5B0ID%5B5FD2DA60262617429607E459C0E09D92%5D%5D>

Adverse events will be assessed for [¹⁸F]Flutemetamol immediately following the imaging scan. Additionally, a follow-up telephone call will be made to each participant within 1 day following their imaging scan. If the participant cannot be contacted at 1 day post-scanning, then we will continue trying to contact them for up to 7 days post-scanning.

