APPENDIX I: GE Healthcare Supplemental Safety Reporting Form

SUPPLEMENTAL SAFETY CRF

IS& ID	SUBJECT NO.	GEHC MDx Product:
[]	[]	[]

Effective Date: 21-Feb-2013

Date of Birth	Gender (check one)
[]	 Male  Female
D D M M M M	 White  Black or African American
Y Y Y Y Y Y	 Hispanic or Latino  Not Hispanic or Latino
	1 2
	3 4
	5 6
	7 8
	9 10
	11 12
	13 14
	15 16
	17 18
	19 20
	21 22
	23 24
	25 26
	27 28
	29 30
	31 32
	33 34
	35 36
	37 38
	39 40
	41 42
	43 44
	45 46
	47 48
	49 50
	51 52
	53 54
	55 56
	57 58
	59 60
	61 62
	63 64
	65 66
	67 68
	69 70
	71 72
	73 74
	75 76
	77 78
	79 80
	81 82
	83 84
	85 86
	87 88
	89 90
	91 92
	93 94
	95 96
	97 98
	99 100

PRE-TREATMENT EVENTS AND TREATMENT-EMERGENT EVENTS

Record AEs outcomes or attribution to agent. Serious AEs should be reported to GE within 24hrs using the SAE form provided in your ISS Site Manual.

Event No.	Event (Record diagnosis in Standard Medical Terminology) (Record One Event Per Line) Be as specific as possible, for example: Infection = NOT SPECIFIC Upper respiratory infection = SPECIFIC	Date / Time of Dose Administration	Date / Time of Onset	Date / Time of Resolution	Intensity	Relationship to IMP	Treatment Given	Action Taken With Study Treatment	Outcome of Adverse Event			
									1=Yes** 2=No	1=Not Related 2=Related	1=Resolved 2=Not Resolved 3=Fatal 4=Unknown	1=Yes** 2=No
1.												
2.												
3.												

**If treatment given, specify:

D D M M M M	Y Y Y Y Y Y
[]	[]
H H	M M

D D M M M M	Y Y Y Y Y Y
[]	[]
H H	M M

D D M M M M	Y Y Y Y Y Y
[]	[]
H H	M M

**If treatment given, specify:

D D M M M M	Y Y Y Y Y Y
[]	[]
H H	M M

D D M M M M	Y Y Y Y Y Y
[]	[]
H H	M M

**If treatment given, specify:

D D M M M M	Y Y Y Y Y Y
[]	[]
H H	M M

Date: [] [] [] [] [] []

Primary Investigator/Designee's Signature: _____

SAE defined as: Any event that resulted in death, was immediately life-threatening, required inpatient hospitalization or prolongation of existing hospitalization, resulted in persistent or significant disability or incapacity, was a congenital anomaly or birth defect, or required medical or surgical intervention to prevent one of the outcomes listed above.

Significant events which when based on appropriate medical judgment may jeopardize the subject and may require medical/surgical intervention to prevent one of the outcomes listed above.

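### The Appendix E symptom form is given only after flutemetamol injection and has no onset field, so symptoms already present can be logged as possible tracer events

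*Combined protocol and SAP*

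**What the plan says.** Every scheduled flutemetamol safety contact comes after injection. The Appendix D footnote to the questionnaire row reads "Performed immediately after [¹⁸F]Flutemetamol study". Section 11 states: "Adverse events will be assessed for [¹⁸F]Flutemetamol immediately following the imaging scan". Both places add a telephone contact ("A follow-up telephone call will be made to each participant within 1 day following their imaging scan"), with attempts continuing for up to 7 days. The heading of Appendix E places the form at the end of the infusion instead.

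Appendix E is a yes/no list of symptoms with a comment column. Its last block includes paired rows on numbness, weakness and burning in the feet and in the fingers, for example "Numbness of fingers/hands". There is no headache row and no row for other symptoms; the nearest is the row beginning "Pain (Other site".

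Appendix I, the supplemental safety form, is headed "PRE-TREATMENT EVENTS AND TREATMENT-EMERGENT EVENTS" and asks for the date and time of dosing and of onset for each event. Under Section 8.3 each patient "must have completed adjuvant chemotherapy more than 6 months ago, but no more than 36 months prior to initial study scan". On earlier human use, Section 4.2.1 says of ALZ101: "The most frequent AE was 'headache' (2 subjects"), out of 23 dosed.

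**The concern.** A symptom list given once, after exposure, shows what is present but not what is new. Several of the listed symptoms could plausibly remain from chemotherapy. A woman with long-standing numbness would truthfully answer yes, and nothing on the form prompts anyone to ask when it began. Appendix I needs that onset time, and Sections 11.1 and 11.2 limit required reporting to events within 24 hours of injection, so onset also decides whether an event is reportable. At stake is the quality of the safety listing in a study of up to 15 women, where a few misdated entries would be a visible share of the record.

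**Working it through.** **1. When symptoms are asked about.** Appendix D has four columns: screening, the MRI and neuropsychology session, and two PET visits. The questionnaire is marked only under the PET visits, with the footnote placing it after the flutemetamol study. The telephone call is later still. Pre-injection symptom checks scheduled: none.

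**2. Items on Appendix E.** Body as a whole 5 + cardiovascular 1 + digestive 3 + respiratory 1 + skin 5 + central nervous system 7 = 22. Limb items: numbness 2 + weakness 2 + burning 2 = 6. Share: 6/22 = 27%.

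**3. Whether another form supplies the baseline.**

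| Form | Asks for onset, or whether present before dosing? | Scheduled before injection? |
|---|---|---|
| Appendix E | No; yes/no and free comment only | No |
| Appendix B | No; toxicities, including neuropathy, listed by current drug | Not in Appendix D |
| Appendix I | Yes; dose time and onset time per event | Not in Appendix D |
| Appendix H (serious events) | Yes; a before-administration option | Serious events only |

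Appendix B is organised by current drugs, whereas chemotherapy ended more than 6 months earlier, and it does not cover the 22 items. Appendix I asks the right question, but no text says how an Appendix E answer reaches it, and Appendix E does not collect the onset time it needs.

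**4. The protocol's own illustration of why a baseline matters.** In ALZ102 (Section 4.2.2), 5 subjects had a QTc above 440 ms after injection. Three of them also had one before injection, so 5 − 3 = 2 were new. Without the pre-injection reading all 5 would have looked new.

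**5. Headache.** ALZ101: 2/23 = 8.7%, which reproduces the stated 9% for nervous-system events (exact 95% interval 1.1% to 28.0%). The agent was [¹¹C]Flutemetamol, with or without [¹⁸F]AH110691. ALZ102 lists no headache in 19 subjects. ALZ103, described as the first use of [¹⁸F]Flutemetamol, lists none in 22; the exact upper 95% limit is 1 − 0.025^(1/22) = 15.4%. In-study events across the three studies: 4 + 3 + 2 = 9, with headache and QT prolongation at 2 each.

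**6. Three timings for one form.** Appendix E says the end of the infusion, Appendix D says after the study, and Section 11 says after the scan. Table 4 gives a push of about 30 seconds. The protocol does not state when its own flutemetamol scan starts. If the ALZ103 recommendation were followed (start about 90 minutes after injection, duration about 30), the scan would end at about 90 + 30 = 120 minutes. The earliest and latest readings would then be about two hours apart.

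**The case against.** The strongest reply is that a yes on Appendix E is not a recorded adverse event. The form labels its entries as possible events, gives each row a comment column, and ends with dated and timed lines for the person completing it and for investigator oversight. Appendix I then asks for onset and dose times. This stands in part: a reader might infer that the plan necessarily records old symptoms as adverse events, and the documents do not support that. They show only that separating old from new is left to an unprompted comment and to recall after the scan.

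The effect on expedited reporting is also small. In Table 5, attribution matters for unexpected grade 3 events and for late deaths. Grades 4 and 5 are reported regardless of attribution, and lower-grade events need no expedited report. Nothing shows that residual numbness would reach the cell where attribution decides. This stands.

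Eligibility may remove some affected women. Section 8.4 excludes only neurological disease known to affect cognition, but the Appendix A checklist refers more broadly to other neurological disorders. Neither names peripheral neuropathy, so the overlap is reduced at most.

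A reader might also infer that the form misses the commonest event with this tracer. That is not supported. Headache led only in ALZ101, no event there was judged related, and ALZ103 listed only diarrhea and back pain. The general pain row, the comment column and the telephone call could all capture a headache. Counting how many of the nine earlier events lack a named row does not help either: headache and back pain would have to be treated alike, and the two QT events are ECG findings that no symptom form would detect.

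**Conclusion.** The point holds as a modest gap in safety data collection. The questionnaire has no pre-injection administration, no onset field and no stated link to Appendix I, and 6 of its 22 items (27%) ask about limb symptoms that may predate the tracer. Pre-existing symptoms can therefore be logged as possible tracer events. Headache is unnamed and there is no row for other symptoms, which is a smaller weakness.

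The size cannot be set from the documents, because they give no rate of residual neuropathy. If 10% to 40% is assumed, 15 × 0.10 = 1.5 to 15 × 0.40 = 6 women would be expected to answer yes to a limb item. A reader might take that as a count of false adverse events. It is not one: the rate is an assumption, and a yes still passes through comment and investigator review. Nor do the documents support saying that the safety record will be wrong. The exact binomial test in Section 10.4 and the sample size in Section 10.5 do not depend on this form. It is an improvement worth making because it is cheap.

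**What to change.** - Complete Appendix E just before the flutemetamol injection as well as after it, and add the pre-injection pass to Appendix D.
- Treat as treatment-emergent only a symptom that is new, or worse than the pre-injection answer. Enter pre-injection yes answers on Appendix I as pre-treatment events, and state how answers pass from Appendix E to Appendix I.
- Add an onset-time column and rows for 'Headache' and 'Other (specify)'.
- Reconcile the three stated timings of the post-injection form in Appendix D, Appendix E and Section 11.

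The cost is a second pass of a one-page form at the same visit, about five minutes per patient, and a small form revision. No extra staff or procedure is needed.
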